2.2.1.1. Pharmacokinetic Overview of Ritlecitinib

The PK profile of ritlecitinib is characterized by rapid absorption, rapid elimination ($t_{1/2}$ of ~ 2 hours) and is approximately dose proportional. Steady state generally appears to have been reached by Day 4 for the QD regimens and Day 6 for the BID regimens based on similar median trough (pre-dose) ritlecitinib beyond Day 6. Ritlecitinib has been evaluated at single oral doses ranging from 5 mg to 800 mg and multiple oral doses ranging from 50 mg to 400 mg QD and at 100 mg and 200 mg BID for 14 days. The clearance mechanisms for ritlecitinib in humans appear to be primarily by metabolism. Less than 10% of ritlecitinib is excreted unchanged in the urine.

2.2.1.2. Safety of Ritlecitinib in Adult and Adolescent Participants With AA (Study B7931015)

B7981015 was a Phase 2b/3, randomized, double blind, placebo controlled, dose ranging study to investigate ritlecitinib in both adolescent (\geq 12 to <18 years old) and adult (\geq 18 years old) participants with \geq 50% scalp hair loss due to AA. The study had a maximum duration of approximately 57 weeks. This included an up to 5-week Screening period, a 48-week treatment period, and a 4-week follow up period. The treatment period was comprised of a placebo-controlled period that included a 4-week loading phase and a 20-week maintenance phase, followed by a 24-week extension phase.

Eligible participants were randomized to blinded ritlecitinib and matching placebo in a 2:2:2:2:1:1:1 (200 mg/50 mg, 200 mg/30 mg, 50 mg, 30 mg, 10 mg, placebo-200 mg/50 mg, and placebo-50 mg, respectively) manner for a total of 7 treatment sequences.

The study randomized 105 adolescents (12 to 17 years of age) and the distribution of adolescents across treatment groups was similar.

Ritlecitinib 200/50 mg, 200/30 mg, 50 mg and 30 mg were significantly superior to placebo at Week 24 on clinician-assessed and patient-reported endpoints related to scalp hair regrowth (including response based on absolute SALT \leq 20, response based on absolute SALT \leq 10, and PGI-C response). Exposure response modelling based on SALT \leq 20 and SALT \leq 10 response at Week 24 showed a positive relationship between dose and response. Ritlecitinib 200/50 mg, 200/30 mg, 50 mg and 30 mg were also nominally superior to placebo at Week 24 in producing improvement in eyebrows and eyelashes. Continued improvement in efficacy endpoints was seen between Week 24 and Week 48.

Overall efficacy was similar in adolescents (12 to <18 years of age) and adults (\geq 18 years of age).

The proportion of participants who experienced all-causality TEAEs was similar across treatment groups up to Week 24 (placebo-controlled period) and up to Week 48 (overall). The most frequently reported TEAEs in any group included nasopharyngitis, headache, and upper respiratory tract infection. Up to week 24, the incidence of nasopharyngitis, folliculitis, urticaria, dizziness, upper respiratory tract infection and urinary tract infection was higher in participants treated with ritlecitinib (particularly 200/50 mg and 200/30 mg) than placebo. Most TEAEs were mild to moderate in severity. Fourteen participants experienced 16 SAEs up to Week 48:

- 200/50 mg (4 participants): appendicitis; empyema and sepsis; invasive lobular breast carcinoma, spontaneous abortion.
- 200/30 mg (2 participants): appendicitis; chemical poisoning and suicidal behavior.
- 50 mg (2 participants): breast cancer; pulmonary embolism.
- 30 mg (1 participant): diverticulitis.
- 10 mg (2 participants): suicidal behavior; eczema.
- Placebo-200/50 mg: no SAEs.
- Placebo-50 mg (3 participants): spontaneous abortion; conversion disorder; heavy menstrual bleeding. These treatment-emergent SAEs were all reported during the Placebo-Controlled Period.

Of the 16 SAEs, 12 were considered by the investigator as unrelated to study intervention. The 4 SAEs that were considered related to study intervention in the opinion of the investigator were sepsis and empyema (both in 1 participant); breast cancer; and eczema. There were no deaths in the study.

PFIZER CONFIDENTIAL

Page 24

Treatment with ritlecitinib was associated with changes in hematological parameters, some of which were dose dependent. In the first weeks of the study, there were slight, transient decreases in hemoglobin and small, variable changes in neutrophil and leukocyte levels. Small, early decreases in platelets were observed with ritlecitinib treatment; these levels remained stable up to Week 48. Dose-dependent early decreases in absolute lymphocyte levels, CD3 (T lymphocytes) and T lymphocyte subsets (CD4 and CD8) were observed. There was a dose-dependent early decrease in CD16/56 (NK cells), particularly in groups who had received a 200 mg loading dose of PF-06651600 for 4 weeks. Overall, there were no clinically meaningful effects of ritlecitinib on ALT, AST, bilirubin, or alkaline phosphatase. The incidence of elevation in hepatic enzymes was low and not dose dependent. Up to Week 48, there were no potential Hy's law cases.

Overall, ritlecitinib was safe and well-tolerated in the adolescent population. In general, there was a lower proportion of adolescent participants with SAEs, severe AEs and AEs of interest relative to adult (\geq 18 years of age) participants. The TEAEs suggest there are no risks unique to adolescents, except for a higher frequency of acne in the adolescent patients which is not unexpected considering that acne is generally more common in adolescents than adults.

For a complete description and results of this study, please refer to the current version of the ritlecitinib IB.

2.3. Benefit/Risk Assessment

More detailed information about the known and expected benefits and risks and reasonably expected adverse events of ritlecitinib may be found in the current version of the IB, which is the SRSD for this study.

2.3.1. Risk Assessment

Potential Risk of Clinical Significance	Summary of Data/Rationale for Risk	Mitigation Strategy
	Study Intervention(s) Ritlecitin	nib
 viral reactivation serious infections and opportunistic infections malignancy and lymphoproliferative disorders thromboembolism dermatologic effects (eg. rash, acne, folliculitis, urticaria) reduction in platelet count and lymphocyte count 	Clinical experience with other JAK inhibitors Ritlecitinib clinical studies (B7931005, B7981015, B7981019, B7981032, and B7981037) and pre-clinical studies	Exclusion of participants at risk Short duration of treatment Safety labs at screening, baseline and EOT Visit
S	Study Procedures blood collection	for PK
Extravasation, bruising, local discomfort	Collection of 5 PK samples on Day 7	Use of highly qualified pediatric nurses, with venipuncture experience. When possible, use of IV canula, allowing all 5 samples to be collected with just one venipuncture.

2.3.2. Benefit Assessment

No immediate therapeutic benefits are expected from participation in this study. However, after completion of this study, participants will qualify to be screened for the planned 3-year, long-term, open-label (active dose only) Study B7981028. Dose selection for this planned study will be based on results from Study B7981031, and thus enrollment into the planned long-term study will not occur immediately after Study B7981031. Also, data collected in this study will support dose selection for the planned pediatric safety and efficacy Study B7981027.

2.3.3. Overall Benefit/Risk Conclusion

Taking into account the short treatment duration and the measures to minimize the risk to study participants (through the inclusion/exclusion criteria and safety monitoring), the potential risks identified in association with ritlecitinib are expected to be minimal and justified by the anticipated benefits of informing dose selection in studies evaluating ritlecitinib for the treatment of AA in children.

Objectives	Endpoints			
Primary:	Primary:			
• To characterize the PK of ritlecitinib in children with AA 6 to <12 years of age.	AUC ₂₄ on Day 7			
Secondary:	Secondary:			
• To further characterize the PK of ritlecitinib in children with AA 6 to <12 years of age.	• C_{max} , T_{max} , CL/F , V_Z/F and $t_{\frac{1}{2}}$ on Day 7			
• To characterize the PD of ritlecitinib in children with AA 6 to <12 years of age.	• Change from baseline in interferon gamma IP-10 and lymphocyte subsets (T cell, B cell, and NK cells) on Day 7			
 To evaluate the safety and tolerability of ritlecitinib in children with AA 6 to <12 years of age. 	 TEAE Treatment related AEs. Serious AEs (SAEs) and AEs leading to discontinuation Clinically significant abnormalities in vital signs. Clinically significant abnormalities in clinical laboratory values. 			
• To assess the overall palatability, acceptability, and tolerability of the proposed age appropriate formulation in children with AA aged 6 to <12 years of age.	Taste assessment			

3. OBJECTIVES, ENDPOINTS, AND ESTIMANDS

4. STUDY DESIGN

4.1. Overall Design

This is an interventional, PK, PD, Phase 1, open label study in children 6 to less than 12 years of age with \geq 50% scalp hair loss due to AA. The purpose of the study is to collect data to support dose selection for subsequent studies in the same population.

Participants will be screened and, if all eligibility criteria are met, will receive the first dose of IP within 28 days after the screening visit.

Participants will receive 20 mg ritlecitinib in one dose, daily, for 7 consecutive days. On Day 7 (EOT) blood samples for PK will be collected at:

- 0 hr (pre-dose)
- 0.5 hr,
- 1 hr,
- 3 hrs, and
- 8 hrs after dosing.

At least 12 evaluable participants with respect to the primary endpoint will be enrolled in the study. Participants that are not able to provide a full set of evaluable PK data or that miss more than one dose may be replaced at the discretion of the sponsor.

A follow-up visit will be conducted by phone, 28 to 35 days after the last dose of ritlecitinib.

4.2. Scientific Rationale for Study Design

The PK assessments from this study are necessary to support ritlecitinib dose selection in subsequent studies in children 6 to <12 years of age. The systemic exposure assessments from this study will provide information on whether the selected dose for children 6 to <12 years old provides exposures similar to the proposed dose for adolescents and adults. The PD endpoints of IP-10 and lymphocyte subsets will be assessed to understand if there is any difference in PD responses between children 6 to less than 12 years of age, and adults and adolescents. The open-label, 7-day study design has been reviewed by the US FDA and the EMA and agreed as part of the iPSP and PIP, respectively.

The 20 mg dose selected is predicted to provide exposures in 6 to <12 year old children, similar to the 30 mg dose in adults and adolescents.

The study is designed as a 7 day multiple dose study. Multiple doses are necessary for evaluating steady state PK because ritlecitinib has non stationary PK and steady state is achieved after >4 days of dosing.

PK samples will be collected at times of pre-dose and post-dose times of 0.5, 1, 3 and 8 hours. These sample times were selected to enable estimation of PK parameters of AUC, C_{max} and T_{max} using non-compartmental analysis methods. For calculation of AUC_{tau} at steady state, the predose concentration will be used as an estimate for the concentration of 24 hours post dose.

4.2.1. Patient Input Into Design

Surveys of children and parents were conducted to evaluate preferences and feasibility of the study, including study drug administration, blood draws, and clinic visit duration.

4.2.2. Diversity of Study Population

Reasonable attempts will be made to enroll participants with the distribution of characteristics with respect to race, ethnicity, and age to ensure the study population is representative of the patient population that will use study intervention in clinical practice.

4.2.3. Adjudication Committee

This protocol will use an independent endpoint adjudication committee to determine whether certain investigator-reported events meet the definition of disease-related safety endpoints, using predefined endpoint criteria. Further information about this endpoint adjudication committee is provided in a charter, including a description of the scope of the committee's responsibilities, the process and definitions to be utilized by the committee for adjudication, and communication plan including timelines.

The following adjudication committees are used for the B798 program:

- Opportunistic Infection Review Committee (OIRC),
- Cardiovascular Event Adjudication Committee (CVEAC),
- Malignancy Adjudication Committee (MAC), and
- Neurosafety Event Adjudication Committee (NSEAC).

Events requiring submission to an adjudication/review committee will be identified by:

- Pfizer Study Team or designee during the review of participant data listings or by
- Site monitors during routine monitoring of participant's study records

Additional types of events for review and adjudication may be identified by Pfizer.

The Pfizer Study Team or designee will notify the study site of any such events should they be identified.

The Pfizer Study Team or designee will provide a listing of specific documents needed to support event adjudication by the Adjudication/Review Committees. Obtaining and submitting the documentation will be the responsibility of the study site.

Event documentation will vary with the event requiring adjudication and may include (but not limited to): hospital discharge summaries, operative reports, clinic notes, ECGs, diagnostic tests, pathology reports, autopsy reports and death certificate information, as applicable.

Review of redacted copies of these documents by the Pfizer Study Team or designee may be performed, where ethically and scientifically justified and permitted by local regulations, to ensure completeness and quality of event documentation prior to submission to Adjudication/Review Committees.

4.2.4. E-DMC

This study will use an E-DMC. The E-DMC will be responsible for ongoing monitoring of the safety of participants in the study according to the charter. The recommendations made by the E-DMC will be forwarded to the appropriate authorized Pfizer personnel for review and final decision. Pfizer will communicate such decisions, which may include summaries of aggregate analyses of endpoint events and of safety data that are not endpoints, to regulatory authorities and investigators, as appropriate.

Composition of the E-DMC and the processes under which the E-DMC operates will be documented in the E-DMC charter.

4.2.5. Choice of Contraception/Barrier Requirements

Human reproductive safety data for ritlecitinib are limited and not enough to evaluate the risk for treatment related birth defects. In animal studies (rats and rabbits) fetotoxicity and fetal malformations were observed at exposures equivalent to 49 to 55 times the MRHD. No developmental toxicity was observed at exposures equivalent to 12 to 16 times the MRHD. Although the suspicion for human teratogenicity based on the intended pharmacology of the compound is minimal, the use of a highly effective method of contraception in WOCBP is required (see Appendix 4).

The definition of WOCBP is provided in Section 10.4.3.

4.3. Justification for Dose

The selected dose for Study B7981031 is 20 mg QD. The rationale for this dose selection is as follows.

Study B7981015 was performed in adults and adolescents and evaluated 5 dosing regimens of ritlecitinib:

- 50 mg and 30 mg with and without a loading dose of 200 mg
- A 10 mg dose without loading dose.

The results from the above study indicated that the 10 mg dose did not differentiate from placebo, while the doses of 50 and 30 mg with and without loading dose demonstrated significant efficacy over placebo. The 50 mg dose (without loading dose) was identified as the regimen with optimal benefit:risk for adults and adolescents for registration.

The dose determination to support dosing in this study was based on the following considerations:

1. The systemic exposure data generated in B7981015 for adult and adolescent participants were utilized to derive the dose recommendations for children (6 to <12 years of age) using population PK modeling and simulation analysis.

PFIZER CONFIDENTIAL

Page 30

2. The dose selected for children 6 to <12 years of age in Study B7981031 is expected to provide lower exposures than the 50 mg dose in the B7981015 study in adults and adolescents.

The dose of 20 mg selected for evaluation in this PK, PD study is predicted to provide exposures in children 6 to <12 years of age approximating the exposure of a 30 mg dose in adults and adolescents. The dose of 20 mg is considered to be adequate to meet the objectives of the study to characterize of PK of ritlecitinib in children.

4.4. End of Study Definition

The end of the study is defined as the date of the completion of the last scheduled procedure (as shown in the SoA) for the last participant in the trial, globally.

5. STUDY POPULATION

This study can fulfill its objectives only if appropriate participants are enrolled, including participants across diverse and representative racial and ethnic backgrounds. If a prescreening tool is utilized for study recruitment purposes, it will include collection of information that reflects the enrollment of a diverse participant population including, where permitted under local regulations, age, sex, race, and ethnicity. The following eligibility criteria are designed to select participants for whom participation is considered appropriate for the present study and subsequent screening in the planned long-term study. All relevant medical and nonmedical conditions should be taken into consideration when deciding whether a particular participant is suitable for this protocol.

Prospective approval of protocol deviations to recruitment and enrollment criteria, also known as protocol waivers or exemptions, is not permitted.

Pfizer will review eligibility criteria verified by the investigator or qualified designee to confirm that participants meet study eligibility criteria before they are enrolled into enrolled into the study. The enrollment approval process will be initiated for a participant after an informed consent document has been signed and the investigator or qualified designee has assessed the participant as eligible. The enrollment approval will be based on review of CRF/system data.

There are no enrollment minimums or maximums in any country.

5.1. Inclusion Criteria

Participants are eligible to be included in the study only if all of the following criteria apply:

Age and Sex:

1. Participants who are 6 to <12 years old at the time of the screening visit. Refer to (Section 10.4) for reproductive criteria for male and female participants.

Disease Characteristics:

 A diagnosis of severe AA, including AT and AU, with ≥50% scalp hair loss due to AA (ie, a SALT score of ≥50) at both the Screening and Baseline visits, without evidence of terminal hair regrowth within the previous 12 months.

Other Inclusion Criteria:

3. For study participants in the EU/UK only:

History of clinical response failure to AA treatment (such as topical, off-label pharmacologic, or hairpiece prosthetics)

AND

a. Participants with a history of psychological counseling for AA (as evidenced by Screening AA assessments) in the past year prior to Screening

Participants are eligible if current psychosocial impairment is confirmed by administering all four instruments listed below and meeting the specified thresholds:

- PROMIS® Parent Proxy Anxiety Symptoms: T-score 60-70
- PROMIS® Parent Proxy Depressive Symptoms: T-score 60-70
- BRIEF®2 (BRI, ERI, CRI): T-score 60-70 on any one of the 3 components of the BRIEF®2.
- Modified CDLQI (score of \geq 7)

NOTE: For T-scores higher than 70 (PROMIS and BRIEF) see exclusion criterion 7.

OR

b. Participants with no history of psychological counseling for AA in the past year prior to Screening

In order to be eligible for this study, participants must:

- Have a T-score of 60-70 on any one of the 3 instruments (PROMIS®-Anxiety Symptoms or PROMIS®-Depressive Symptoms or any one of the 3 components of BRIEF®2)
- Complete at least 5 psychological counseling sessions for AA prior to Screening
- Be re-evaluated after completion of the psychological counseling and have a T-score of 60-70 on any one of the three instruments (PROMIS®-Anxiety Symptoms or PROMIS®-Depressive Symptoms or any one of the 3 components of BRIEF®2)

PFIZER CONFIDENTIAL

Page 32

NOTE: For T-scores higher than 70 (PROMIS and BRIEF) see exclusion criterion 7.

5.2. Exclusion Criteria

Participants are excluded from the study if any of the following criteria apply:

Medical Conditions:

- 1. A known congenital cause of AA, other systemic diseases that may cause hair loss (eg, lupus erythematosus, thyroiditis, systemic sclerosis, lichen planus, etc) or other etiology of hair loss (eg, telogen effluvium, androgenetic alopecia, etc).
- 2. Conditions that may impact absorption or metabolism of IP (eg, celiac disease, cholecystectomy or gastrectomy).
- 3. Pre-existing hearing loss, or sudden hearing loss, or middle or inner ear disease such as chronic otitis media, cholesteatoma, Meniere's disease, labyrinthitis, or other auditory condition that is considered acute, fluctuating or progressive. If hearing loss is due to acute otitis media, participants can be rescreened at a later date, once the condition resolves.
- 4. Any present malignancies or history of malignancies, history of any lymphoproliferative disorder such as EBV related lymphoproliferative disorder, history of lymphoma, history of leukemia, or signs and symptoms suggestive of current lymphatic or lymphoid disease,
- 5. Active autoimmune disorder (other than AA), known immunodeficiency disorder, or a first degree relative with a hereditary immunodeficiency.
- 6. History (one or more episodes) of CMV, varicella, herpes zoster (shingles) or disseminated herpes simplex. A history of uncomplicated herpes simplex is not exclusionary.
- 7. Other medical or psychiatric condition (including recent [within the past year] or active suicidal ideation/behavior) that may increase the risk of study participation or, in the investigator's judgment, make the participant inappropriate for the study, including but not limited to:
 - For participants in the EU/UK with scores of >70 on the PROMIS® or any component of the BRIEF®2, or with previous history of suicidal behaviors in the past 5 years ("Yes" answer for events that occurred in the past 5 years) to any of the suicidal behavior items of the C-SSRS or with any lifetime history of serious or recurrent suicidal behavior, a risk assessment must be performed and documented by a qualified mental health professional to assess whether it is safe to participate in the trial.
 - For participants in the US and other non-EU/UK countries with a previous history of suicidal behaviors in the past 5 years ("Yes" answer for events that occurred in the past 5 years) to any of the suicidal behavior items of the C-SSRS or with any lifetime PFIZER CONFIDENTIAL

history of serious or recurrent suicidal behavior, a risk assessment must be performed and documented by a qualified mental health professional to assess whether it is safe to participate in the trial.

- For participants in the US and other non-EU/UK countries: Clinically significant depression per the CDRS-R (T-score ≥40).
- History of or presence of any current major psychiatric disorder that is not explicitly permitted in the inclusion/exclusion criteria.
- 8. Trisomy 21 (EU/UK only)

Prior/Concomitant Therapy:

9. Current use of any prohibited concomitant medication(s) or history of discontinuation of treatment with a JAK inhibitor due to a treatment related adverse event. Refer to Section 6.9.

Prior/Concurrent Clinical Study Experience:

10. Previous administration with an investigational product (drug or vaccine) within 30 days (or as determined by the local requirement) or 5 half-lives preceding the first dose of study intervention used in this study (whichever is longer).

Diagnostic Assessments:

- 11. Any laboratory abnormality that may increase the risk of study participation or, in the investigator's judgment, make the participant inappropriate for the study, including but not limited to the following:
 - Renal dysfunction defined as:
 - eCrCl normalized to BSA: Confirmed eCrCl <60 mL/min/1.73 m² based on Modified Schwartz equation (pediatric patients 2 to <12 years of age). See Appendix 6.
 - Hepatic dysfunction defined as:
 - Total bilirubin >1.5 \times ULN (except for Gilbert's syndrome)
 - AST >1.5 \times ULN
 - ALT >1.5 \times ULN
 - Hematologic abnormalities defined as:
 - Absolute neutrophil count $<1.2 \times 10^{9}/L$ ($<1200/mm^{3}$)

- Hemoglobin <11.0 g/dL
- Platelet count $<150 \times 10^{9}/L$ ($<150,000/mm^{3}$)
- Absolute lymphocyte count of $<0.8 \times 10^9$ /L (<800/mm³)
- Any infection requiring hospitalization, parenteral antimicrobial therapy or judged to be opportunistic by the investigator within the 3 months prior to the first dose of IP or infection with HIV, hepatitis B or hepatitis C viruses according to protocol specific testing algorithms or active acute or chronic infection requiring treatment with oral antibiotics, antivirals, antiparasitics, antiprotozoals, or antifungals within 4 weeks prior to Day 1 or superficial skin infection within 1 week prior to Day 1, or evidence of untreated or inadequately treated active or latent mycobacterium TB infection or a positive QFT test (or equivalent) performed within 3 months prior to first dose of IP. QFT (or equivalent) test should be performed during screening if not performed within past 3 months (see Appendix 9).

NOTE: participants may be rescreened after the infection resolves.

12. Current or recent history of clinically significant severe, progressive, or uncontrolled renal (including but not limited to active renal disease or recent kidney stones), hepatic, hematological, gastrointestinal, metabolic, endocrine (particularly thyroid disease which can be associated with hair loss), pulmonary, cardiovascular, psychiatric, immunologic/rheumatologic or neurologic disease; or have any other severe acute or chronic medical or psychiatric condition or laboratory abnormality that may increase the risk associated with study participation or investigational product administration, or interfere with the interpretation of study results; or in the opinion of the investigator or Pfizer (or designee), the participant is inappropriate for entry into this study, or unwilling/unable to comply with study procedures and lifestyle requirements. Significant trauma or major surgery within 1 month of the first dose of IP is also exclusionary.

Other Exclusion Criteria:

- 13. Not up to date with all age appropriate vaccines, including 2-dose vaccination for varicella, or vaccination with attenuated live vaccine within 6 weeks of first dose of IP.
- 14. Investigator site staff directly involved in the conduct of the study and their family members, site staff otherwise supervised by the investigator, and sponsor and sponsor delegate employees directly involved in the conduct of the study and their family members.

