8.2.1. Rater Qualifications

Clinical evaluations will be completed at screening, for eligibility purposes, as follows:

- SALT score
- Taste Assessment Questionnaire
- The C-SSRS suicidal ideation and behavior risk assessment
- CDRS

• WISC-V (Wechsler Intelligence Scale for Children - 5th edition)

The Taste Assessment questionnaire is a simple assessment that can be conducted by the Study Coordinator or designee.

All other assessments require experienced personnel, with skills in interacting with children. For C-SSRS, specific documented training is required.

Additional details are provided in specific appendices and study manual, for each assessment.

For C-SSRS assessments, only qualified raters will be allowed to evaluate and/or rate participants in this study (see Appendix 11 for details).

Training material will be provided to each site, as appropriate. The level of experience with the target population (or equivalent), specific scale experience (or equivalent), and certification required (if applicable) will be listed and used to determine whether a rater is approved for a given assessment. The rater must become certified to perform selected study assessments before they can participate in the conduct of the study. For specifically defined assessments, rater training and standardization exercises may be conducted, and written documentation will be provided by the site for each rater's certification. In return, each site will be provided written documentation outlining each rater's certification for specific study assessments. Recertification may be required at periodic intervals during the study. The raters who administer specific study assessments will be documented in a centralized location and all site staff who administer ratings will be verified in the site study documentation during the conduct of the study.

To ensure consistency and reduce variability, each participant should have all assessments conducted by the same rater. Every effort will be made to have all assessments completed by the same rater.

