10.12. Appendix 12 – CDRS-R

The CDRS-R is a brief 17-item rating scale for diagnosing depression and assessing its severity. The scale is designed for use in 6- to 12-year-old children. Individuals are rated on seventeen symptom areas, including dysfunction relating to schoolwork, interpersonal relationships, psychosomatic complaints, and other thoughts and feelings commonly presenting in depressed children and adolescents. Scores are determined by a clinician through a semi-structured interview with the child and parent.³⁹ Interviews take about 10-15 minutes to complete and score. Each item score ranges from 1 to 5 or 1 to 7. Possible total scores ranging from 17 to 113.

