10.13. Appendix 13.1 – PROMIS[®] Parent Proxy Short Form v2.0 – Anxiety 8a

The PROMIS Parent Proxy Short Form v2.0 - Anxiety 8a is an 8-item measure of anxiety. Each item has five response options ranging in value from 1 to 5. Raw scores are calculated by summing the values of the response to each question. The lowest possible raw score for this measure is 8 and the highest possible raw score is 40. Raw scores are transformed to T-scores using a conversion table available from the developer.⁴⁰

T-score rescales the raw score into a standardized score with a mean of 50 and a SD of 10. Therefore, a person with a T-score of 60 is one SD above the pediatric population mean, and a T-Score of 70 is two SDs above the pediatric population mean of 50. PROMIS T-scores 70 or greater are considered severe dysfunction; T-scores from 60 to 69 are considered moderate dysfunction (PROMIS 2020a).⁴⁰

10.13.1. Appendix 13.2 – PROMIS[®] Parent Proxy Short Form v2.0 – Depressive Symptoms 6a

The PROMIS Parent Proxy Short Form v2.0 – Depressive Symptoms 6a is a 6-item measure of depressive symptoms. Each item has five response options ranging in value from 1 to 5. Raw scores are calculated by summing the values of the response to each question. The lowest possible raw score for this measure is 6 and the highest possible raw score is 40. Raw scores are transformed to T-scores using a conversion table available from the developer.⁴⁰

T-score rescales the raw score into a standardized score with a mean of 50 and a SD of 10. Therefore, a person with a T-score of 60 is one SD above the pediatric population mean, and a T-Score of 70 is two SDs above the pediatric population mean of 50. PROMIS T-scores 70 or greater are considered severe dysfunction; T-scores from 60 to 69 are considered moderate dysfunction (PROMIS 2020a).⁴⁰

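### The CDRS-R depression exclusion outside the EU/UK (T-score of 40 or more) does not fit its label on the usual T-score metric, and Appendix 12 describes only a raw total

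*Protocol*

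**What the plan says.** Protocol Section 5.2, criterion 7, lists among the psychiatric exclusions, for the US and other non-EU/UK countries: "Clinically significant depression per the CDRS-R (T-score ≥40"). The key exclusion criteria in the synopsis (Section 1.1) give the same value and the same label. The Schedule of Activities places the CDRS-R at screening for these countries.

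Section 8.1 sends the reader to Appendices 11 to 15 for the psychological assessments. Appendix 12 covers the CDRS-R: 17 items, each scored 1 to 5 or 1 to 7, and "Possible total scores ranging from 17 to 113". It gives no T-score, norm, conversion or cut-off. Section 8.2.1 adds that "Additional details are provided in specific appendices and study manual, for each assessment".

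The only T-score metric printed in the protocol is in the PROMIS appendices (10.13 and 10.13.1): "T-score rescales the raw score into a standardized score with a mean of 50 and a SD of 10". There, "T-scores from 60 to 69 are considered moderate dysfunction". The EU/UK entry criterion in Section 5.1 includes "PROMIS® Parent Proxy Depressive Symptoms: T-score 60-70".

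On enforcement, Section 5 states: "Prospective approval of protocol deviations to recruitment and enrollment criteria, also known as protocol waivers or exemptions, is not permitted".

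**The concern.** The criterion joins three things: a label (clinically significant depression), a metric (T-score) and a value (40 or more). On the ordinary T-score scale, 40 is below average, so the label does not describe the children whom the rule would catch. The appendix that should explain the scale speaks only of a raw total, and 40 is a legitimate value there too. A site working from the protocol alone cannot tell which scale the number belongs to.

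Two consequences are possible. A site that applies the rule as written, on the usual metric, would turn away children with average scores. A site that compares the raw total with 40 would depart from the written criterion and could classify the same child differently from the first site. Waivers are barred, and criterion 7 is not among the criteria that Section 5.4 lists for rescreening, so a child excluded in this way has no stated route back.

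**Working it through.** The plan gives no derivation of the value 40, so there is no figure to reproduce. The related figures can be checked.

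**1. Raw range in Appendix 12.** With 17 items scored at least 1, the minimum is 17 × 1 = 17. If k items run to 5 and 17 − k run to 7, the maximum is 5k + 7(17 − k) = 119 − 2k. Setting this equal to 113 gives k = 3: 3 × 5 + 14 × 7 = 15 + 98 = 113. The printed range is therefore a raw total, and 40 lies inside it.

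**2. The protocol's own T-score metric (PROMIS only).** z = (T − 50)/10. T = 60 gives z = +1 and T = 70 gives z = +2, as the PROMIS appendices state.

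**3. The same metric applied to 40 (assumption for the CDRS-R, roughly normal scores).** z = (40 − 50)/10 = −1.0. P(T ≥ 40) = 1 − Φ(−1.0) = 0.841. By comparison, P(T ≥ 60) = 0.159 and P(T ≥ 70) = 0.023.

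**4. Sensitivity to the assumed mean and SD.**

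| Assumed mean | SD 8 | SD 10 | SD 12 |
|---|---|---|---|
| 45 | 73% | 69% | 66% |
| 50 | 89% | 84% | 80% |
| 55 | 97% | 93% | 89% |

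Every cell puts the mean above 40, so a majority at or above 40 is built in. The table shows how the share moves if the scale is centred near 50. It is not evidence that the scale is centred there.

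**5. What would make the label fit.** For 40 to lie even one SD above the mean, the mean would have to be 40 − 8 = 32, 40 − 10 = 30 or 40 − 12 = 28 for SDs of 8, 10 and 12. At mean 30, SD 10, the share at or above 40 is 16%. The documents state no such norm for the CDRS-R, but they do not state mean 50 for it either.

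**6. Raw-total reading.** The documents give no distribution of raw totals, so the excluded share cannot be computed.

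**The case against.** The strongest reply is that no passage contradicts another. The synopsis and criterion 7 agree, Appendix 12 is merely silent on T-scores, and an instrument can have both a raw total and a T-score, as PROMIS does. The mean of 50 and SD of 10 are not stated for the CDRS-R. Appendix 14 also prints no T-score norm for the BRIEF2, although the BRIEF2 is used with T-score limits, so an unprinted norm alone would be missing detail. The study manual, or the source cited in Appendix 12, may hold the conversion.

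Most of this stands, and it narrows the point. What remains is that a value of 40, called a T-score and labelled clinically significant depression, does not fit on the usual meaning of a T-score. A conversion table in a manual would not alter the printed label and value. The BRIEF2 limits of 60 to 70 raise no such difficulty on that metric.

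The consequence is also bounded. Criterion 7 is not an exhaustive list and allows investigator judgment, and criterion 12 covers psychiatric disease, so the CDRS-R value is the only numeric depression cut-off and not the only test. The sponsor reviews eligibility before enrolment (Section 5), and the investigator logs reasons for screening failure (Section 8.1). The sponsor review starts only once the investigator has judged a child eligible, so it is the log that would show wrongful exclusions. The target is 12 evaluable participants, and "There are no enrollment minimums or maximums in any country", so recruitment can shift between regions.

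A reader might infer that 40 was certainly meant as a raw total. The text says T-score, and nothing in the documents shows otherwise. A reader might also set the EU/UK PROMIS band of 60 to 70 against the CDRS-R value as a contradiction. PROMIS is a different, parent-reported instrument, so the comparison is context and not proof.

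**Conclusion.** The point holds as a mismatch between label, metric and value that the protocol does not resolve. Two facts need no assumption: the criterion uses a T-score, and the appendix for that scale describes only a raw total on which 40 is also possible. The claim that 40 is below average rests on the assumed mean of 50 and SD of 10, under which about 84% of a reference population would meet the exclusion.

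It is tempting to read that share as an expected screen-failure rate. The documents do not support this: the norm is assumed, and the share describes a reference population and not children screened with severe alopecia areata. Nor do they support any effect on the primary endpoint. The criterion acts on eligibility outside the EU/UK, and the AUC24 analysis is unaffected. If the cut-off is too low, it excludes too many children; it does not admit children at risk.

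This should be fixed because it is an eligibility threshold without waivers and the correction is cheap. Confidence is medium, since the study manual has not been seen.

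**What to change.** The sponsor should check the source of the value and establish whether 40 was meant as a raw total or a T-score. Then, by amendment, reconcile the synopsis, Section 5.2 criterion 7 and Appendix 12 so that label, metric and value agree. If the T-score is kept, Appendix 12 should state its norm or conversion and the cut-off should be confirmed on it; otherwise the metric or the value should be corrected. The study manual and the CRF field should use the same metric. The value is for the sponsor to set, and none is proposed here.

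The cost is wording in up to three places and a check of the manual and CRF field. No procedures, visits or participants are added.
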